7.1.2 Secondary outcomes

(1) Proportion of patients with END (Δ NIHSS ≥ 2 and Δ NIHSS ≥ 4) at 24 hours after randomization.

Δ NIHSS indicates 24-hour NIHSS score minus post-IVT NIHSS score.

(2) Proportion of patients with cerebrovascular events within 1 day, 7 days and 90 days after randomization. Cerebrovascular events included progressive stroke (NIHSS deterioration ≥ 2 scores),

transient ischemic attack or new ischemic lesions confirmed by imaging.

(3) NIHSS scores at 7 days.

(4) Proportion of patients with mRS 0-2 at 30 days.

(5) mRS distribution at 30 days and 90 days.

(6) BI scores at 30 days and 90 days.

(7) Proportion of the patients with BI 60-100 at 30 days and 90 days.

(8) Peripheral blood inflammatory indices, including neutrophil-to-lymphocyte ratio (NLR), platelet-to-lymphocyte (PLR), lymphocyte-to-monocyte (LMR) and (platelet \times neutrophil)/lymphocyte (SII) at 24-48 hours after randomization.

(9) Laboratory examinations (S100- β , BDNF, and MPO) at 24-48 hours after randomization.

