7.2 Safety outcomes

(1) The ejection fraction evaluated by ultrasonic cardiogram within 72 hours.

[figure not shown]
(2) Death rate within 90 days.

(3) Intracranial hemorrhage and symptomatic intracranial hemorrhage within 7 days.

(4) Blood pressure fluctuation within 24 hours.

(5) Infarction edema volume evaluated by cranial CT at 24 hours.

8. Study flow diagram

AIS: acute ischemic stroke; IVT: intravenous thrombolysis; NS: normal saline.

9. Study periods

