9.4 Follow-up periods

Neurological measurements including mRS score and Barthel index are assessed via a telephone interview at 30 and 90 days. Cerebrovascular events and death events are recorded carefully at this time. All the adverse events should be recorded and tracked until properly resolved.

10. Adverse events monitoring

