11.2 Statistical analysis

The modified intention-to-treat analysis of efficacy outcomes and safety outcomes are performed on the full analysis set, which is composed of all patients who receive randomization independent of treatment and at least 1 efficacy evaluation after enrollment. The primary outcome is also performed with sensitivity analyses, including per-protocol analysis; imputation of missing primary outcome data under the scenarios of worst possible outcome, and best possible outcome. The χ^2 test is used in the unadjusted analysis. Modified Poisson regression model with robust error estimation is used in analysis of the primary outcome and other dichotomous end points, with adjustment for prespecified covariates

(age, sex, post-IVT NIHSS scores and onset-to-needle time). The relative risk (RR) with their 95% confidence interval (95%CI) is calculated in both unadjusted and adjusted analysis. Generalized linear models (GLMs) are conducted for analyse continuous end points, including NIHSS scores, Barthel scale, blood pressure, infarction volumes, ejection fraction at each follow-up time point. The full range score on mRS is analyzed by an ordinal logistic-regression model, and odds ratio (OR) with 95%CI are calculated. Cox regression model are used for analyzing the follow-up cerebrovascular events, presented with cumulative probability of events in Kaplan Meier cures. No interim analyses are performed in this study. The missing values of baseline variables in the covariate-adjusted analyses are replaced by mean values (continous variates) or mode (dichotomous variates) only if the number of them account for less than 10% in total.

A 2-sided P value <0.05 is considered statistical significance. Because multiple comparisons potentially cause type I error, findings for secondary outcome analyses should be interpreted as exploratory. SPSS software (version 26, IBM) and R software (version 4.1.0) are used for the statistical analyses.

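### The Kaplan-Meier curve for cerebrovascular events gives death no role, so with deaths censored it would modestly overstate the cumulative probability it claims to show

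*Combined protocol and SAP*

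**What the plan says.** Two analyses of the same events are planned.

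- **Time to event.** Section 11.2: "Cox regression model are used for analyzing the follow-up cerebrovascular events, presented with cumulative probability of events in Kaplan Meier cures".
- **Proportions.** Section 7.1.2 lists "Proportion of patients with cerebrovascular events within 1 day, 7 days and 90 days after randomization". These are binary, so they fall under the general rule in 11.2: "Modified Poisson regression model with robust error estimation is used in analysis of the primary outcome and other dichotomous end points".

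The event is defined in 7.1.2: "Cerebrovascular events included progressive stroke" (NIHSS worsening of two points or more), "transient ischemic attack or new ischemic lesions confirmed by imaging". Death is not among the components. It is a separate safety outcome in 7.2, "Death rate within 90 days", and is collected at the 30- and 90-day telephone contacts described in 9.4: "Cerebrovascular events and death events are recorded carefully at this time".

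The plan gives no censoring rule for the Cox and Kaplan-Meier analysis and names no competing-risk method. It does not say whether a fatal stroke is an event, or what status a patient who dies without an event has in the proportions. The only rule for missing outcomes in 11.2, "imputation of missing primary outcome data under the scenarios of worst possible outcome, and best possible outcome", covers the primary outcome. Section 11.2 also says that secondary findings are to be read as exploratory.

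**The concern.** The plan promises a cumulative probability, which is an absolute risk among the patients actually randomised. A patient who has died can no longer have a cerebrovascular event. Kaplan-Meier for a single event type has no state for death, so in ordinary use such a patient is censored. The estimator then treats the patient as if the same future event risk as the survivors still applied. One minus Kaplan-Meier therefore describes risk in a hypothetical population in which nobody dies first, and it lies above the actual risk whenever event-free deaths occur while others are still at risk.

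Two things follow. The right-hand end of the curve and the 90-day proportion may disagree in the same report, with nothing in the plan to explain why. And because the rule is unstated, it would be chosen at analysis, possibly after the data have been seen.

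A separate question of interpretation concerns the proportion itself. An arm with more early deaths has fewer patients left to have events, so its event proportion can be slightly lower without any event being prevented. This matters for a trial whose own withdrawal criteria (3.2.3) and adverse-event list (10.1) anticipate acute heart failure and pulmonary edema.

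**Working it through.** **The plan's figures.** The plan gives no event or death rate, so it has no figure of its own to reproduce on this point. Its only computed number is 120 per group (11.1). That follows from the unpooled formula: (1.960 + 0.842)² × (0.673×0.327 + 0.493×0.507) / 0.18² gives 114, and 114/0.95 = 120. It is used below only as the arm size.

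**Assumed inputs (not from the documents).** Let *e* be the true 90-day cumulative incidence of a first event, 10%, 20% or 30%. Let *d* be the cumulative incidence of death without a prior event, 2%, 5%, 10% or 15%. There is no other censoring.

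**Constant hazards.** The total cumulative hazard is H = −ln(1 − e − d), and the event share is H_e = H × e/(e + d). With deaths censored, 1 − KM = 1 − exp(−H_e). The Aalen-Johansen estimate targets *e* itself, and with complete follow-up it equals the simple proportion with event-free deaths kept in the denominator.

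Example, e = 20% and d = 15%: H = −ln(0.65) = 0.431; H_e = 0.431 × 20/35 = 0.246; 1 − KM = 21.8%, an excess of 1.8 points.

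Value of 1 − KM in %, with the excess in points in brackets:

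| True event risk | d = 2% | d = 5% | d = 10% | d = 15% |
|---|---|---|---|---|
| 10% | 10.1 (0.10) | 10.3 (0.27) | 10.6 (0.56) | 10.9 (0.87) |
| 20% | 20.2 (0.22) | 20.6 (0.56) | 21.2 (1.16) | 21.8 (1.82) |
| 30% | 30.3 (0.34) | 30.9 (0.87) | 31.8 (1.83) | 32.9 (2.87) |

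**Other timings.** If 80% of events occur before any death, the excess over the same grid is 0.02 to 0.71 points. At the extreme where every death precedes every event, 1 − KM = e/(1 − d), and the excess is 0.2 to 5.3 points (30%/0.85 = 35.3% at the top).

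**What the silence allows.** Take e = 20% and d = 15% under constant hazards. Counting event-free deaths as non-events gives a proportion of 20.0%. The Kaplan-Meier curve ends at 21.8%. Dropping those deaths as missing gives 20%/0.85 = 23.5%.

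**Between arms.** If the true risk is 20% in both arms but event-free deaths are 5% and 15%, the curves end at 20.6% and 21.8%, about 1.3 points apart.

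**The proportion.** Give both arms the same event hazard, with 1 − KM = 18.1%, so H_e = −ln(0.819) = 0.200. Let 7% and 18% die first. The death hazards H_d that satisfy H_d/(H_e + H_d) × [1 − exp(−(H_e + H_d))] = 7% and 18% are about 0.080 and 0.220. The event proportions, H_e/(H_e + H_d) × [1 − exp(−(H_e + H_d))], are then 17.4% and 16.3%. The arm with more deaths shows 1.1 points fewer events although its event hazard is the same. With 120 per arm, the standard error of a difference near 17% is √(2 × 0.17 × 0.83/120) = 4.8 points, so this is about 0.2 standard errors.

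**The case against.** The strongest reply is that a reader might infer a contradiction that the plan does not contain: deaths censored in one analysis, counted as event-free in the other, and so handled in opposite ways. Neither rule is written down. Both are common defaults, and event-free deaths could equally be dropped as missing. That is correct. What the documents show is a named estimator that does not suit its stated target under the usual default, together with an unstated rule.

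A reader might also infer that the Cox comparison is wrong. It is not: with deaths censored it estimates a cause-specific hazard ratio, which is a legitimate quantity.

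Nor should one infer that a better curve removes the impression of benefit in an arm with more deaths. In the contrast above, Kaplan-Meier shows 18.1% in both arms, while an Aalen-Johansen curve would show the same 17.4% and 16.3% as the proportions. That issue is met only by reporting death alongside and adding the composite.

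Three further points limit the size. A two-point NIHSS worsening already counts as an event, so many patients who deteriorate before dying will have had one, and deaths after a first event do not affect the curve. If fatal strokes count as events, fewer deaths compete. And a large imbalance in deaths would be seen elsewhere: death is a safety outcome and is grade 6 on the mRS, and 7% v 18% is about 8 v 22 of 120 (uncorrected chi-square p about 0.006). All three stand, and they are why the point is minor. The exploratory label does not answer it, because that label concerns multiplicity and not which quantity a curve estimates.

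**Conclusion.** The point holds as a minor one. Section 11.2 names Kaplan-Meier for a cumulative probability, the event excludes death, and death has no role in the analysis. If deaths are censored, the curve is too high in every scenario examined where event-free deaths occur. The likely size is small: 0.1 to 2.9 points under constant hazards, below 1 point if most events come early, and 5.3 points at an extreme bound. These figures rest on assumed rates, because the documents give none. The comparative Cox result, the primary outcome and the sample size are unaffected. The tendency of the event proportion to fall in an arm with more early deaths is a separate matter, about 1 point in a deliberately wide contrast, and it belongs to the choice of endpoint and not to the curve.

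**What to change.** In section 11.2:

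1. Replace the Kaplan-Meier curve with the Aalen-Johansen cumulative incidence of a first cerebrovascular event, with death without a prior event as the competing event. Show the cumulative incidence of that death beside it.
2. Label the Cox result a cause-specific hazard ratio, with censoring at death stated, and report the cause-specific hazard ratio for death next to it.
3. State, here or in 7.1.2, whether a fatal stroke counts as an event.
4. Keep event-free deaths in the denominator of the 1-, 7- and 90-day proportions, and add *cerebrovascular event or death* as a supporting proportion.

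The cost is a few lines of SAP text and standard code in R, which the plan already names. Deaths are already recorded under 9.4; it is worth confirming that the case report form captures their dates. The report gains one curve and one table row. Sample size and trial conduct do not change.

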11.3 Analysis population

11.3.1 Intention-To-Treat (ITT)

The ITT population involves all participants in the groups to which they are originally assigned, regardless of whether they complete the treatment or adhere to the protocol. It can reflect the real-world effectiveness of the treatment and remain unbiased by the participants' adherence to the treatment plan.

11.3.2 Per protocol (PP)

The PP population involves the participants who fully complete the treatment and adhere to the protocol. It can be used to assess the efficacy of the treatment on those who followed the prescribed procedures.

11.3.3 Safety population

The safety population included all participants who receive the protocol treatment and have at least one time of safety evaluation.

12. Data management and monitoring

12.1 Case Report Forms (CRF)

A CRF should be completed and signed by the investigators for each participant randomized. The

reasons for subject withdrawing from the study must be noted on the CRF. Adverse events and its follow-up interviewing should be recorded carefully on the CRF. All forms should be completed within 1 week after subject visit. The investigators should ensure the accuracy, completeness, legibility and timeliness of the data submitted to the sponsor in the CRF and in all required reports.

Appendix

Appendix 1: National Institutes of Health Stroke Scale (NIHSS)

Instructions	Scale Definition	Score

1a. Level of Consciousness: The investigator must choose a response if a full evaluation is prevented by such obstacles as an endotracheal tube, language barrier, orotracheal trauma/bandages. A 3 is scored only if the patient makes no movement (other than reflexive posturing) in response to noxious stimulation.
	
0 = Alert; keenly responsive.
 
1 = Not alert; but arousable by minor stimulation to obey, answer, or respond.
 
2 = Not alert; requires repeated stimulation to attend, or is obtunded and requires strong or painful stimulation to make movements (not stereotyped).
 
3 = Responds only with reflex motor or autonomic effects or totally unresponsive, flaccid, and flexic.
	

1b. LOC Questions: The patient is asked the month and his/her age. The answer must be correct - there is no partial credit for being close. Aphasic and stuporous patients who do not comprehend the questions will score 2. Patients unable to speak because of endotracheal intubation, orotracheal trauma, severe dysarthria from any cause, language barrier, or any other problem not secondary to aphasia are given a 1. It is important that only the initial answer be graded and that the examiner not "help" the patient with verbal or non-verbal cues.
	
0 = Answers both questions correctly.
 
1 = Answers one question correctly.
 
2 = Answers neither question correctly.
	

1c. LOC Commands: The patient is asked to open and close the eyes and then to grip and release the non-paretic hand. Substitute another one step command if the hands cannot be used. Credit is given if an unequivocal attempt is made but
	
0 = Performs both tasks correctly.
 
1 = Performs one task correctly.
 
2 = Performs neither task correctly.
	

not completed due to weakness. If the patient does not respond to command, the task should be demonstrated to him or her (pantomime), and the result scored (i.e., follows none, one or two commands). Patients with trauma, amputation, or other physical impediments should be given suitable one-step commands. Only the first attempt is scored.
	

2. Best Gaze: Only horizontal eye movements will be tested. Voluntary or reflexive (oculocephalic) eye movements will be scored, but caloric testing is not done. If the patient has a conjugate deviation of the eyes that can be overcome by voluntary or reflexive activity, the score will be 1. If a patient has an isolated peripheral nerve paresis (CN III, IV or VI), score a 1. Gaze is testable in all aphasic patients. Patients with ocular trauma, bandages, pre-existing blindness, or other disorder of visual acuity or fields should be tested with reflexive movements, and a choice made by the investigator. Establishing eye contact and then moving about the patient from side to side will occasionally clarify the presence of a partial gaze palsy.
	
0 = Normal. 1 = Partial gaze palsy; gaze is abnormal in one or both eyes, but forced deviation or total gaze paresis is not present. 2 = Forced deviation, or total gaze paresis not overcome by the oculocephalic maneuver.

3. Visual: Visual fields (upper and lower quadrants) are tested by confrontation, using finger counting or visual threat, as appropriate. Patients may be encouraged, but if they look at the side of the moving fingers appropriately, this can be scored as normal. If there is unilateral blindness or enucleation, visual fields in the remaining eye are scored. Score 1 only if a clear-cut asymmetry, including quadrantanopia, is found. If
	
0 = No visual loss. 1 = Partial hemianopia. 2 = Complete hemianopia. 3 = Bilateral hemianopia (blind including cortical blindness).

patient is blind from any cause, score 3. Double simultaneous stimulation is performed at this point. If there is extinction, patient receives a 1, and the results are used to respond to item 11.
		

4. Facial Palsy: Ask – or use pantomime to encourage – the patient to show teeth or raise eyebrows and close eyes. Score symmetry of grimace in response to noxious stimuli in the poorly responsive or non-comprehending patient. If facial trauma/bandages, orotracheal tube, tape or other physical barriers obscure the face, these should be removed to the extent possible.
	
0 = Normal symmetrical movements.
 
1 = Minor paralysis (flattened nasolabial fold, asymmetry on smiling).
 
2 = Partial paralysis (total or near-total paralysis of lower face).
 
3 = Complete paralysis of one or both sides (absence of facial movement in the upper and lower face).
	

5. Motor Arm: The limb is placed in the appropriate position: extend the arms (palms down) 90 degrees (if sitting) or 45 degrees (if supine). Drift is scored if the arm falls before 10 seconds. The aphasic patient is encouraged using urgency in the voice and pantomime, but not noxious stimulation. Each limb is tested in turn, beginning with the non-paretic arm. Only in the case of amputation or joint fusion at the shoulder, the examiner should record the score as untestable (UN), and clearly write the explanation for this choice.
	
0 = No drift; limb holds 90 (or 45) degrees for full 10 seconds.
 
1 = Drift; limb holds 90 (or 45) degrees, but drifts down before full 10 seconds; does not hit bed or other support.
 
2 = Some effort against gravity; limb cannot get to or maintain (if cued) 90 (or 45) degrees, drifts down to bed, but has some effort against gravity.
 
3 = No effort against gravity; limb falls.
 
4 = No movement.
 
UN = Amputation or joint fusion, explain:
 <hr/> 
5a. Left Arm
 
5b. Right Arm
	

6. Motor Leg: The limb is placed in the appropriate position: hold the leg at 30 degrees (always tested supine). Drift is scored if the leg falls before 5 seconds. The aphasic patient is encouraged using urgency in the voice and pantomime, but not noxious stimulation. Each limb is tested in turn, beginning with the non-paretic leg. Only in the case of amputation or joint fusion at the hip, the examiner should record the score as untestable (UN), and clearly write the explanation for this choice.
	
0 = No drift; leg holds 30-degree position for full 5 seconds.
 
1 = Drift; leg falls by the end of the 5-second period but does not hit bed.
 
2 = Some effort against gravity; leg falls to bed by 5 seconds, but has some effort against gravity.
 
3 = No effort against gravity; leg falls to bed immediately.
 
4 = No movement.
 
UN = Amputation or joint fusion, explain:
 
_____
 
6a. Left Leg
 
6b. Right Leg


7. Limb Ataxia: This item is aimed at finding evidence of a unilateral cerebellar lesion. Test with eyes open. In case of visual defect, ensure testing is done in intact visual field. The finger-nose-finger and heel-shin tests are performed on both sides, and ataxia is scored only if present out of proportion to weakness. Ataxia is absent in the patient who cannot understand or is paralyzed. Only in the case of amputation or joint fusion, the examiner should record the score as untestable (UN), and clearly write the explanation for this choice. In case of blindness, test by having the patient touch nose from extended arm position.
	
0 = Absent.
 
1 = Present in one limb.
 
2 = Present in two limbs.
 
UN = Amputation or joint fusion, explain:
 
_____
 
_____

8. Sensory: Sensation or grimace to pinprick when tested, or withdrawal from noxious stimulus in the obtunded or aphasic patient. Only sensory loss attributed to stroke is scored as abnormal and the examiner should test as many body areas (arms [not hands], legs, trunk, face) as needed to accurately check for hemisensory loss. A score of 2, “severe or total sensory loss,” should only be given when a severe or total loss of sensation can be clearly demonstrated. Stuporous and aphasic patients will, therefore, probably score 1 or 0. The patient with brainstem stroke who has bilateral loss of sensation is scored 2. If the patient does not respond and is quadriplegic, score 2. Patients in a coma (item 1a=3) are automatically given a 2 on this item.
	
0 = Normal; no sensory loss.
 
1 = Mild-to-moderate sensory loss; patient feels pinprick is less sharp or is dull on the affected side; or there is a loss of superficial pain with pinprick, but patient is aware of being touched.
 
2 = Severe to total sensory loss; patient is not aware of being touched in the face, arm, and leg.


9. Best Language: A great deal of information about comprehension will be obtained during the preceding sections of the examination. For this scale item, the patient is asked to describe what is happening in the attached picture, to name the items on the attached naming sheet and to read from the attached list of sentences. Comprehension is judged from responses here, as well as to all of the commands in the preceding general neurological exam. If visual loss interferes with the tests, ask the patient to identify objects placed in the hand, repeat, and produce speech. The intubated patient should be asked to write. The patient in a coma (item 1a=3) will automatically score 3 on this item. The examiner must choose a score for the patient with stupor
	
0 = No aphasia; normal.
 
1 = Mild-to-moderate aphasia; some obvious loss of fluency or facility of comprehension, without significant limitation on ideas expressed or form of expression. Reduction of speech and/or comprehension, however, makes conversation about provided materials difficult or impossible. For example, in conversation about provided materials, examiner can identify picture or naming card content from patient’s response.
 
2 = Severe aphasia; all communication is through

or limited cooperation, but a score of 3 should be used only if the patient is mute and follows no one-step commands.
	
fragmentary expression; great need for inference, questioning, and guessing by the listener. Range of information that can be exchanged is limited; listener carries burden of communication. Examiner cannot identify materials provided from patient response.
 
3 = Mute, global aphasia; no usable speech or auditory comprehension.
	

10. Dysarthria: If patient is thought to be normal, an adequate sample of speech must be obtained by asking patient to read or repeat words from the attached list. If the patient has severe aphasia, the clarity of articulation of spontaneous speech can be rated. Only if the patient is intubated or has other physical barriers to producing speech, the examiner should record the score as untestable (UN), and clearly write an explanation for this choice. Do not tell the patient why he or she is being tested.
	
0 = Normal.
 
1 = Mild-to-moderate dysarthria; patient slurs at least some words and, at worst, can be understood with some difficulty.
 
2 = Severe dysarthria; patient's speech is so slurred as to be unintelligible in the absence of or out of proportion to any dysphasia, or is mute/anarthric.
 
UN = Intubated or other physical barrier, explain: _____
	

11. Extinction and Inattention (formerly Neglect): Sufficient information to identify neglect may be obtained during the prior testing. If the patient has a severe visual loss preventing visual double simultaneous stimulation, and the cutaneous stimuli are normal, the score is normal. If the patient has aphasia but does appear to attend to both sides, the score is normal. The presence of visual spatial neglect or anosagnosia may also be taken as evidence of
	
0 = No abnormality.
 
1 = Visual, tactile, auditory, spatial, or personal inattention or extinction to bilateral simultaneous stimulation in one of the sensory modalities.
 
2 = Profound hemi-inattention or extinction to more than one modality; does not recognize own hand or orients to only one side of space.
	

abnormality. Since the abnormality is scored only if present, the item is never untestable.		
	Total NIHSS:	

